3.3 Safety and Risk Profile

The safety and risk profile of the RhinAer procedure will be evaluated with respect to overall incidence of adverse events and treatment-related adverse events.

4.0 Study Plan

4.1 Study Design

The study is designed as a multicenter (up to 20 sites), prospective, open-label, single-arm study in up to 140 participants.

All participants will be evaluated prior to treatment and following treatment at week 13 (3 months). The 3-month evaluation will occur in the physician's office and be used for the primary analysis.

The study will have additional follow-up evaluations at 6, 12, 24, and 36 months conducted by phone interview to provide additional information on longer-term safety and duration of treatment effect.

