5.6 Follow-up Evaluations

Follow-up visit dates will be calculated from the study procedure date. Follow-up visits should be scheduled within the specified visit windows described in Section 5.1 and Table 1 (Section 8.3.2). The office follow-up evaluation occurs at 13 weeks after the procedure. Evaluations at 6, 12, 24, and 36 months will be conducted remotely by telephone assessment by site personnel. The timing of all follow-up evaluations is based on the date of the procedure and should not be altered based on the actual time of preceding follow-up visits. Participants who make nonstudy visits should be evaluated for possible adverse events and an Adverse Event CRF should be submitted if appropriate.

RhinAer RELIEF single arm protocol Rev C Final 27JAN2021CONFIDENTIAL

All participants should be followed through the final evaluation visit at 3 years postprocedure regardless of their success/failure classification at previous evaluations. Every effort should be made to avoid having participants withdraw from the study (Section 9.5). If a participant does choose to withdraw from the study, it is very important to record information regarding the reason(s) and the last known status of the participant.

The following assessments will be conducted as indicated for each follow-up time point and recorded on the corresponding CRFs:

Office evaluation at 13-week (3-month) follow-up

- Nasal assessment (each nostril) including photos or video
- Current use of medication, devices or other therapies for symptoms of chronic rhinitis, including medication name, frequency, and dose
- Participant reported change in use of as needed medications and devices for chronic rhinitis symptoms (completed by participant)
- rTNSS (completed by participant)
- Cough and postnasal drip symptoms (completed by participant)
- MiniRQLQ (completed by participant)
- VAS pain score (completed by participant)
- Adverse events.

Remote (telephone) evaluations: 6-month (26-week), 12-month (52-week), 24-month (104-week), and 36-month (156-week) follow-up

- rTNSS (verbal administration by site personnel)
- Cough and postnasal drip symptoms (verbal administration by site personnel) (no 2-week)
- MiniRQLQ (verbal administration by site personnel)
- Participant reported change in use of as needed medications and devices for chronic rhinitis symptoms (verbal administration by site personnel)
- Patient satisfaction survey (verbal administration by site personnel)

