6.3 Sample Size Estimate

The study will enroll up to 140 participants. The power analysis was performed such that there is adequate power to reject the null hypothesis that the mean improvement from baseline in rTNSS is 1 point or less. Sample size estimation was based on a paired t-test for change from baseline at 13 weeks using the following assumptions:

- Significance level $\alpha = 0.025$ (one-sided)
- Power = 90%
- $\mu_d = 1$ -point decrease in mean change score = MCID
- SD = 3 = estimated standard deviation of the mean difference based on an observed SD of 2.6 in a prior study.

RhinAer RELIEF single arm protocol Rev C Final 27JAN2021CONFIDENTIAL

The minimum number of subjects to achieve 90% power is 97 (G-Power, paired ttest). Allowing for 15% loss (nonevaluable) and adjusting for a balanced distribution across 20 sites the sample size is 140 participants. It is anticipated that participants will be enrolled at sites on a competitive basis; however, a reasonable balance of participants among sites may be maintained by potentially capping enrollment at individual sites based on the final number of participating sites.

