6.6 Missing Data

All efforts will be made to collect all data points in this study. Missing data will be imputed for the primary endpoint by assuming the missing outcomes represent no change from baseline. Additional post hoc sensitivity analyses may be performed if missing cases exceed 10% of the sample size, including a worst-case analysis (all missing rTNSS at 3 months are the worst possible score), to further assess the effect of missing data on the primary analysis. The results of the sensitivity analysis will not be used to adjust the conclusions drawn from the primary analysis.

Secondary outcome measures and additional observational measurements will be analyzed by using available data only.

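### The 3-month primary evaluation has no remote fallback, although the same questionnaires are given by phone at four later visits; adding one is a cheap way to avoid imputed zeros

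*Combined protocol and SAP*

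**What the plan says.** Section 4.1 sets the place of the primary evaluation: "The 3-month evaluation will occur in the physician's office and be used for the primary analysis". Section 5.6 repeats it: "The office follow-up evaluation occurs at 13 weeks after the procedure". The schedule in 5.1 puts the 3-month column under the in-office heading with a ±14-day window, against ±30 days for every later visit. Table 1 in 8.3.2 also labels the 13-week visit as an office visit.

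For the later visits, 5.6 says: "Evaluations at 6, 12, 24, and 36 months will be conducted remotely by telephone assessment by site personnel". The same section gives the mode of each questionnaire. At 3 months the entry is "rTNSS (completed by participant"; at the remote visits the entries are "rTNSS (verbal administration by site personnel" and "MiniRQLQ (verbal administration by site personnel". Section 4.7 already assigns site staff to remote follow-up.

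On missing values, 6.6 says: "Missing data will be imputed for the primary endpoint by assuming the missing outcomes represent no change from baseline". Secondary measures use available data only. Sections 6.6 and 9.6 promise effort to obtain data, but neither names another mode for the 3-month scores.

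**The concern.** The rTNSS, the responder status derived from it, and the MiniRQLQ are participant reports that need no examination, and the study already has a telephone process for them. Yet at the one time point that decides study success (4.5.3), the protocol gives sites no written route other than attendance. If a participant cannot come in within the window and the site does not phone off-protocol, a score that could have been observed becomes an imputed zero for the primary endpoint. The same person drops out of the responder and MiniRQLQ results.

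Analysis will not repair this. The sensitivity analyses in 6.6 are optional, are considered only above 10% missing, and may not alter the primary conclusion. Better collection is the direct remedy.

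**Working it through.** **Plan's own figure.** Section 6.3 uses one-sided α = 0.025, 90% power, a 1-point difference and SD 3. The exact paired t-test (noncentral t) gives n = 97 with power 90.1%, so the stated 97 reproduces. Allowing for 15% loss, 97 / 0.85 = 114.1, or 115; the plan attributes the rise to 140 to balance across sites as well.

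Section 6.3 labels the 1-point decrease as both the assumed change and the MCID. Read literally against the 1-point null of 6.2, power would equal α (2.5%). The 97 is reproduced only if the true mean decrease lies 1 point beyond the null, that is, at 2 points. The 2-point scenario below is therefore an inference.

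**Model for the zero rule.** Let a fraction m of the N = 140 have an imputed change of 0. Let the rest have mean improvement μ and standard deviation SD. Assume that those missed would have had the same mean improvement as those seen. Then

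- mean = (1 − m)μ
- variance = (1 − m)SD² + m(1 − m)μ²

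**Scenario A: prior-study figures.** μ = 5.1 (section 1.0, 12 weeks) and SD = 2.6 (section 6.3).

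| m | Mean | SD |
|---|---|---|
| 0 | 5.10 | 2.60 |
| 5% | 0.95 × 5.1 = 4.85 | 2.77 |
| 7.5% | 0.925 × 5.1 = 4.72 | 2.84 |
| 15% | 0.85 × 5.1 = 4.34 | 3.01 |

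For m = 15%, variance = 0.85 × 6.76 + 0.1275 × 26.01 = 9.06, so SD = 3.01.

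The gain from recovering half of the missed visits is:

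- 15% to 7.5%: 0.075 × 5.1 = 0.38 points
- 5% to 2.5%: 0.025 × 5.1 = 0.13 points

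Power against the 1-point null is about 100% for every m up to 20%. At m = 15% the standard error is 3.01 / √140 = 0.254, so the lower confidence limit for the improvement is about 3.8, far above 1.

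**Scenario B: inferred design effect.** μ = 2, SD = 3, N = 140.

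| m | Mean | Power against 1 point |
|---|---|---|
| 0 | 2.00 | 97.5% |
| 5% | 1.90 | 94.7% |
| 7.5% | 1.85 | 92.6% |
| 10% | 1.80 | 89.8% |
| 15% | 1.70 | 82.1% |

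Halving a 15% miss rate raises power from 82.1% to 92.6%.

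**What is assumed.** The documents give no rate of missed 3-month visits and no share that a call would recover. The 5% to 15% range and the one-half recovery are illustrations. The 15% is borrowed from the general loss allowance in 6.3.

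**The case against.** The office visit has good reasons. Endoscopic assessment and images are required at 3 months and are done by the treating physician (4.4.1, 4.7). Baseline and 3-month rTNSS are both self-completed, so the paired difference uses one mode. A phone fallback brings verbal answers to site staff into the primary endpoint of an open-label, single-arm study. The protocol also supports attendance: the visit is booked before the participant leaves (5.5), completed questionnaires are reimbursed (9.4), and loss to follow-up requires three documented contact attempts (9.6). All of this stands. It supports keeping the office visit as the default, but it does not explain why an imputed zero is preferable to a flagged phone score.

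A reader might infer more than the documents support:

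- **That remote collection is barred.** Section 4.1 says where the visit will take place. It does not forbid a call, and no analysis rule excludes a phoned score. Such a score would be a deviation, but still data.
- **That declining the endoscopy forfeits the score.** Section 5.6 lists the questionnaires separately, so a participant can attend, decline the scope and still complete them.
- **That 3-month safety data are lost.** Adverse events are monitored from enrollment to exit (7.1.2) and at nonstudy visits (5.6). Only the scheduled 3-month enquiry is missed.
- **That the whole dilution is due to the visit format.** Section 6.3 says only "Allowing for 15% loss (nonevaluable", and nothing ties that loss to missed visits. The total dilution at 5% to 15% missing is 0.05 × 5.1 = 0.26 to 0.15 × 5.1 = 0.77 points, but a fallback recovers only part of it. The rest comes from the zero-change rule and from participants who cannot be reached.

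**Conclusion.** The gap is real, and closing it is a cheap improvement; the design is not invalid without it. The 3-month scores have one specified route, an established alternative is not offered, and the missing-data rule turns each avoidable miss into a zero.

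The likely benefit is modest: about 0.13 to 0.38 points on the primary estimate under the prior-study effect, if half of 5% to 15% missed visits are recovered and those participants improved like the rest. A reader might conclude that study success is at risk. At the prior-study effect it is not, and the zero rule generally works against the device. Power matters only if the true effect is much smaller, as in the inferred 2-point scenario, where power at N = 140 stays at 90% only up to about 10% missing.

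**What to change.** In 4.1, 5.1 and 5.6, keep the office visit as the default and add a fallback. If the participant cannot attend within the 3-month window, site staff collect the following remotely within that same window: rTNSS, cough and postnasal drip, MiniRQLQ, change in as-needed medication or device use, the satisfaction survey (which 5.1 schedules at 3 months), medication use and adverse events. Record the mode on form 03. State that the nasal assessment, the images and the VAS pain score are then missing; the VAS is a mark on a 100 mm line and no remote visit collects it.

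In section 6, state that remote 3-month scores enter the primary and secondary analyses, and prespecify a sensitivity analysis restricted to in-office scores.

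The cost is a short protocol addition, one form field and one extra analysis; the phone process and staff already exist. The downside is that a few 3-month scores would be given verbally to site staff while baseline scores are self-completed. The mode flag and the in-office analysis make any effect of that visible.

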4.2 Study Population

The target population for this study is adults who have exhibited symptoms of chronic rhinitis, such as congestion, rhinorrhea, sneezing, and itching, that may be caused by nonallergic or allergic triggers for at least 6 months. Patients with symptoms due only to seasonal allergies are to be excluded. This study requires significant symptoms demonstrated by an rTNSS ≥ 6 , which includes moderate to severe symptoms of rhinorrhea and mild to severe symptoms of nasal congestion.

Patients who have anatomic obstructions that may limit access to the target treatment area or have altered posterior nasal anatomy due to prior surgery or injury are excluded from participation.

Patients must meet all inclusion and exclusion criteria listed below for participation in the study.

4.2.1 Inclusion Criteria

- 1. Age 18 to 85 years (inclusively).
- 2. Willing and able to provide informed consent.
- 3. Willing and able to comply with the participant-specific requirements outlined in the Study Protocol.
- 4. Seeking treatment for chronic rhinitis symptoms of at least 6 months duration and willing to undergo an office-based procedure.
- 5. Moderate to severe symptoms of rhinorrhea (rTNSS rating of 2 or 3 for rhinorrhea).
- 6. Mild to severe symptoms of nasal congestion (rTNSS rating of 1, 2 or 3 for congestion).
- 7. $rTNSS \ge 6$.

4.2.2 Exclusion Criteria

1. Anatomic obstructions that in the investigator's opinion limit access to the posterior nasal passage.

RhinAer RELIEF single arm protocol Rev C Final 27JAN2021CONFIDENTIAL

- 2. Altered anatomy of the posterior nose as a result of prior sinus or nasal surgery or injury.
- 3. Active nasal or sinus infection.
- 4. History of significant dry eye.
- 5. History of any of the following: chronic epistaxis, documented episodes of significant nose bleeds in the past 3 months, rhinitis medicamentosa, head or neck irradiation.
- 6. Have rhinitis symptoms only on a seasonal basis due to allergies.
- 7. Known or suspected allergies or contraindications to the anesthetic agents and/or antibiotic medications to be used during the study procedure session.
- 8. Known or suspected to be pregnant or is lactating.
- 9. Participating in another clinical research study.
- 10. Has any condition that predisposes to excessive bleeding.
- 11. Is taking anticoagulants (eg, warfarin, Plavix) or 325 mg aspirin that cannot be discontinued before the procedure.
- 12. Has previous procedure or surgery for chronic rhinitis.
- 13. Other medical conditions which in the opinion of the investigator would predispose the subject to poor wound healing, increased surgical risk, or poor compliance with the requirements of the study.

4.3 Enrollment

Patients diagnosed with chronic rhinitis and meeting all eligibility criteria may be enrolled in the study.

4.4 Outcome Measures

4.4.1 Nasal Assessment

The target PNN area within each nostril will be visually assessed at baseline (pretreatment), immediately following the treatment procedure, and at 3-month evaluation. The use of an endoscope for visual assessment is required. Observations are categorized as not present, mild, moderate, or severe. Representative still photographs or video of each nostril will be captured at each visit.

Assessments include:

- Significant dry eye (yes/no)
- Bruising around orbital area
- Soreness, pain
- Numbness

Endoscope required:

- Inflammation / generalized redness
- Swelling, edema
- Bleeding at anesthetic injection site (not requiring physician intervention)
- Bleeding at treatment site (not requiring physician intervention)
- Nasal obstruction from tissue edema
- Disruption of mucosal flow / crusting.

4.4.2 Pain – Visual Analog Scale Pain Score

A horizontal 100 mm VAS¹⁴ anchored on the left with the words "No Pain" and on the right with the words "Worst Pain Imaginable", will be used to measure nasal pain associated with the procedure. Scores are obtained by measuring the distance in millimeters from the left origin of the line (0) to the point indicated with a slash placed by the participant to indicate their current level of pain in and around the nose.

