
RhinAer RELIEF single arm protocol Rev C Final 27JAN2021CONFIDENTIAL

All participants will be evaluated prior to treatment and following treatment at week 13 (3 months). The 3-month evaluation will be used for the primary endpoint analysis.

The study will have an extended follow-up phase with evaluations conducted at 26 weeks (6 months), 52 weeks (12 months), 104 weeks (24 months) and 156 weeks (36 months) to provide additional information on longer-term efficacy and duration of treatment effect.

StudyThe primary objective is to assess the performance of the RhinAerObjective:procedure with respect to mean change in the 24-hour reflective Total
Nasal Symptom Score (rTNSS) at 3 months posttreatment when used as
a treatment for chronic rhinitis. A secondary objective is the evaluation
of treatment effect duration through an extended follow-up to 36 months.

PrimaryMean change in the 24-hour rTNSS from baseline to 3 months after the**Endpoint:**study procedure.

- Participant responder percentage, defined as the proportion of participants achieving a successful outcome at the 3-month evaluation. A successful outcome is defined as a 30% improvement (decrease) in the rTNSS.
 - Mean change in the Mini Rhinoconjunctivitis Quality of Life Questionnaire (MiniRQLQ) score from baseline to 3 months after the study procedure.
 - Frequency of device-related and procedure-related serious adverse events through the 3-month evaluation.

OtherAdverse events - Incidence (type and category) of adverse events overallOutcomeand by follow-up interval.

Measures: Nasal Assessment – The target posterior nasal nerve area within each nostril will be visually assessed at baseline, following the treatment procedure and at 3 months. The use of an endoscope for visual assessment is required. Representative still photographs or video of each nostril will be captured for each assessment.

Visual analog scale (VAS) for pain - perception of pain associated with the procedure on a 0 to 100 mm scale (0 indicating no pain and 100 indicating the worst pain ever) assessed posttreatment and at 3 months.

rTNSS:

- rTNSS mean and change from baseline at the 3-, 6-, 12-, 24- and 36-month follow-up evaluations.
- rTNSS Individual Nasal Symptom Scores (rhinorrhea, nasal congestion, nasal itching, and sneezing) at baseline and at the 3-, 6-, 12-, 24-month and 36-month follow-up evaluations.

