3.2 Secondary Objectives

Additional objectives include assessment and comparison of secondary endpoints and informational outcome measures.

Secondary endpoints are:

- Participant responder percentage at 3 months. Individual participant success (responder) is defined as at least 30% improvement (decrease) in the 24-hour reflective Total Nasal Symptom Score (rTNSS).
- Mean change in the Mini Rhinoconjunctivitis Quality of Life Questionnaire (MiniRQLQ) score from baseline to 3 months after the study procedure.
- Frequency of device-related and procedure-related serious adverse events through the 3-month evaluation.

Informational outcomes include:

- Adverse events Incidence (type and category) of adverse events overall and by follow-up interval.
- Nasal Assessment The target PNN area within each nostril will be visually assessed at baseline and following the treatment procedure at all evaluations. The use of an endoscope for visual assessment is required. Representative still photographs or video of each nostril will be captured at each visit.

RhinAer RELIEF single arm protocol Rev C Final 27JAN2021CONFIDENTIAL

- Visual analog scale (VAS) for pain perception of pain associated with the procedure on a 0 to 100 mm scale with 0 indicating no pain and 100 indicating the worst pain ever posttreatment through 3 months.
- rTNSS:
 - rTNSS mean and change from baseline at the 3-, 6-, 12-, 24-, and 36month follow-up evaluations.
 - rTNSS Individual Nasal Symptom Scores (rhinorrhea, nasal congestion, nasal itching, and sneezing) at baseline and the 3-, 6-, 12-, 24-, and 36-month follow-up evaluations.
 - Proportion of responders based on improvement in rTNSS at the 3-, 6-, 12-, 24-, and 36-month follow-up evaluations.
- MiniRQLQ:
 - MiniRQLQ mean and change from baseline at the 3-, 6-, 12-, 24-, and 36-month follow-up evaluation.
 - MiniRQLQ domain scores (activity limitations, practical problems, nose symptoms, eye symptoms, and other symptoms) at baseline and the 3-, 6-, 12-, 24-, and 36-month follow-up evaluations.
- Participant satisfaction assessment Five-question self-reported survey of satisfaction with the procedure and recommendation to others summarized by question at the 3-, 6-, 12-, 24-, and 36-month follow-up evaluations.

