5.1 Schedule of Events

		Treatment		Follow-up					
		Irea	i i catillent		In office Rem			ote	
	Screening	Procedure	Immediate Postprocedure	3 Months ¹ (13 weeks)	6 Months (26 weeks)	12 Months (52 weeks)	24 Months (104 weeks)	36 Months (156 weeks)	
Window (days)	(-30)	(0)	(0)	(± 14)	(± 30)	(± 30)	(± 30)	(± 30)	
Activity / Assessment									
Eligibility	Х								
Consent	Х								
Demographics / Medical History	Х								
Physician Evaluations									
Nasal assessment (physical, endoscopic)	Х	Х	Х	Х					
Current medication use (study relevant)	Х	Х	Х	Х	Х	Х	Х	Х	
Participant Evaluations									
VAS nasal pain			Х	Х					
Rhinitis symptoms (rTNSS, cough, and postnasal drip)	Х			Х	Х	Х	Х	Х	
MiniRQLQ	Х			Х	Х	Х	Х	Х	
Participant Satisfaction Survey				Х	Х	Х	Х	Х	
Adverse Events	Х	Х	Х	Х	Х	Х	Х	Х	

¹Primary analysis endpoint.

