No repeat ("touch-up") procedures will be permitted during the study follow-up period.

Procedure data collection

Data relating to the procedure and the products used will be recorded on the Procedure CRF. The following information will be recorded:

• Date of procedure

- Preprocedure nasal assessment (each nostril) including photos or video (physical and endoscopic)
- Preprocedure and procedure medications
- RhinAer Stylus and Aerin Console information
- Aerin Console settings
- Procedure start and end times
- Number of sites treated
- Occurrence of device malfunction, protocol deviation, or adverse events.

5.5 **Postprocedure Assessments and Care**

An endoscopic nasal assessment will be conducted prior to discharging the participant and reported on the Procedure CRF.

Participants will be asked to indicate the pain level experienced during the study procedure from anesthesia delivery to procedure completion using the VAS pain score instrument (vertical line marked on the 100 mm line) on the Pain VAS CRF.

At the discretion of the physician, the following care may be provided:

- Apply compression to the treatment area internally for 5 minutes.
- Apply petroleum jelly to the treatment area as needed.
- Use of nasal saline spray or ointment as needed.
- The participant should be instructed not to blow their nose for 24 hours.

Participants should have their 3-month follow-up visit (13 weeks) scheduled within the visit window prior to release.

Participants should not generally receive other concomitant nasal treatment therapies or interventions after the procedure or during the study follow-up period to avoid confounding the evaluation of the effect of the treatment, unless the additional care is in response to an adverse event or is considered in the best interest of the participant. Therapies, interventions, and pain medication will be monitored at follow-up evaluations.

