6.12 Other Outcome Measures Analyses

Additional outcome measures will be collected for information and hypothesis generating purposes. The primary analysis methods will be descriptive and exploratory and presented by evaluation to more completely understand the time course of treatment effect. Measures will be summarized using frequencies and percentages for categorical measures and mean, median, standard deviation, minimum and maximum for continuous factors. Confidence intervals will be included where appropriate. Statistical comparisons will either not be performed or used for information purposes. Proportions may be compared using t-tests, ANOVA or nonparametric equivalents. Repeated measures ANOVA or mixed effects modeling may be used for longitudinal analysis across evaluations.

Other outcome measures include:

- Nasal Assessment The visual physical and endoscopic assessment factors will be summarized to include frequency and percentage of responses in each category for each component of the nasal assessment at baseline, just prior to treatment, immediately after treatment, and at 3 months after the procedure.
- Visual analog scale (VAS) for pain Summary will include mean VAS pain scores assessed posttreatment and at 3 months.
- rTNSS The rTNSS and its individual components will be subject to multiple summary methods and analyses including the:
 - Mean and mean change from baseline at the 3-, 6-, 12-, 24-, and 36month follow-up evaluations.
 - Mean, mean change from baseline, and response distribution of the 4 components of the rTNSS (rhinorrhea, nasal congestion, nasal itching, and sneezing) at baseline and the 3-, 6-, 12-, 24-, and 36-month follow-up evaluations.

RhinAer RELIEF single arm protocol Rev C Final 27JAN2021CONFIDENTIAL

- Proportion of responders based on 30% improvement in rTNSS at the 3-, 6-, 12-, 24-, and 36-month follow-up evaluations.
- Other rhinitis symptoms (cough and postnasal drip) Mean, mean change from baseline, and distribution of the 4 response categories (0-3 points) at baseline and the 3-, 6-, 12-, 24-, and 36-month follow-up evaluations.
- MiniRQLQ: The MiniRQLQ and its individual components will be subject to multiple summary methods and analyses including the:
 - MiniRQLQ mean and mean change from baseline at the 3-, 6-, 12-, 24-, and 36-month follow-up evaluations.

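### With no pain VAS before the procedure, a sizeable 3-month VAS mean could not be attributed to the procedure

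*Combined protocol and SAP*

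**What the plan says.** Section 4.4.2 gives the purpose of the VAS: it "will be used to measure nasal pain associated with the procedure". The same section defines the score by a slash "placed by the participant to indicate their current level of pain in and around the nose".

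In the Schedule of Events (5.1), the row "VAS nasal pain" is marked under Immediate Postprocedure and 3 Months only. The Protocol Summary gives the timing as "assessed posttreatment and at 3 months". Section 3.2 describes the scale as 0 to 100 mm with "100 indicating the worst pain ever posttreatment through 3 months".

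For the treatment day, section 5.5 asks a different question: "Participants will be asked to indicate the pain level experienced during the study procedure from anesthesia delivery to procedure completion using the VAS" instrument.

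The analysis in 6.12 is descriptive: "Summary will include mean VAS pain scores assessed posttreatment and at 3 months". No change from a pre-procedure value is planned.

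**The concern.** The stated purpose ties the score to the procedure, but the score as 4.4.2 defines it is not limited to pain that the procedure caused. To read a current-pain score at 3 months as procedural pain, one needs either the same participants' scores before treatment or a comparison group. The plan has neither for the VAS. It does take pretreatment values for its other repeated symptom measures (rTNSS, cough, postnasal drip, MiniRQLQ).

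At stake is the reading of one tolerability result. If the 3-month mean were clearly above zero, the report could not say whether it reflected lasting procedural pain, pain that was there before, or a fall from a higher level. The VAS is also the plan's only continuous pain score marked by the participant. Section 7.1.2 does not require postprocedure pain regarded as normal recovery to be reported as an adverse event.

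**Working it through.** The documents give no VAS mean or SD, so there is no figure to reproduce. The check is a cross-reading of the sections that fix the timing and meaning of the score.

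**1. Timing**

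| Source | Before procedure | After procedure | 3 months |
|---|---|---|---|
| Protocol Summary, other outcome measures | no | yes | yes |
| 5.1 Schedule of Events | no (Screening and Procedure columns blank) | yes | yes |
| 5.3 pretreatment data list | no | – | – |
| 5.5 Postprocedure Assessments | – | yes | – |
| 5.6 follow-up list | – | – | yes |
| 8.3.2 Table 1 | no (Screening / Baseline lists 01, 02, 04, 11, 14) | 06A, 06B at Treatment Procedure | 06A, 06B |
| 6.12 analysis | no | yes | yes |

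Every source agrees: 0 VAS assessments before the procedure and 2 after it. The wording in 3.2, which runs from posttreatment through 3 months, adds none before it.

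**2. Can the treatment-day score serve as the baseline?** No. Under 5.5 it recalls pain felt during the procedure, including anesthesia. It answers a different question from current pain, and it refers to a period after treatment had begun.

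**3. Can the nasal assessment serve?** In part. Section 4.4.1 lists a soreness/pain item graded in four categories (absent to severe). Section 6.12 reports those categories at baseline, just before treatment, immediately after it and at 3 months. That is a genuine before-and-after comparison on its own scale. It is coarse, and no planned analysis links it to the VAS.

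**4. What can a 3-month score show alone?** Suppose the mark S covers all current nasal pain, with S = P + O, where P is remaining procedural pain, O is any other nasal pain, and neither is negative. Then 0 ≤ P ≤ S for each participant, and the same holds for the means.

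- If the mean of S is near 0, the mean of P is also near 0. No baseline is needed for that conclusion.
- If the mean of S is sizeable, the mean of P may lie anywhere from 0 to that value.

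**5. Illustration with assumed values (none are in the documents).** Take a 3-month mean of 8 mm.

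| Assumed pre-procedure mean | Change = 3-month − pre-procedure |
|---|---|
| 0 mm | 8 − 0 = +8 mm |
| 8 mm | 8 − 8 = 0 mm |
| 15 mm | 8 − 15 = −7 mm |

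The 3-month summary planned in 6.12 would be the same 8 mm in all three cases.

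**The case against.** **Nothing in the trial's success depends on this.** The VAS is informational, with no hypothesis, threshold or claimed change from baseline. This stands, and it sets the level of importance.

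**The treatment-day score already serves the stated purpose.** This stands for that score, which its wording ties to the procedure. It does not help the 3-month score.

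**Pain is already tracked before and after.** The four-level item is reported before treatment and at 3 months, and under 4.9.1 soreness or pain that needs mitigation or exceeds what was anticipated becomes an adverse event, with causality graded under 7.1.1. This stands in part. It limits what could be missed, but it does not make the VAS mean attributable.

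**Pre-existing nasal pain is not documented.** The symptoms listed in 1.0 and 4.2 do not include nasal pain, the rTNSS has no pain item, and active nasal or sinus infection is excluded. This stands as a caution: pre-existing pain is a possibility that the plan cannot rule out, not an established fact. A reader might infer that participants are selected for 6 months of moderate to severe nasal symptoms. Section 4.2.1 does not say that. It requires chronic rhinitis symptoms for at least 6 months and, separately, a rhinorrhea rating of 2 or 3, a congestion rating of 1 to 3, and an rTNSS of at least 6.

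**The meaning of the 3-month score is uncertain.** The Protocol Summary describes the VAS at both time points as perceived pain linked to the procedure, and the text of form 06A is not in the documents. This also stands. If the 3-month form asks specifically about procedural pain, the participant makes the attribution and 4.4.2 misdescribes the score. Either way the wording needs reconciling.

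**Conclusion.** The point holds in limited form. The VAS is taken twice after treatment and never before it, in a single-arm study. A sizeable 3-month mean, read as current pain under 4.4.2, therefore could not be attributed to the procedure.

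A reader might go further and call any nonzero 3-month mean uninterpretable. The documents do not support that: a low mean bounds the procedural pain that can remain. The bound assumes that the participant marks all current nasal pain, as 4.4.2 describes.

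No size in millimetres can be given, because the documents contain no VAS data. The primary and secondary endpoints and the sample size are unaffected. This is a cheap improvement of low materiality.

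**What to change.** - **5.1 and Table 1:** add one VAS line, explicitly worded as current nasal pain, at screening or before anesthesia on the procedure day. Use identical wording at 3 months.
- **4.4.2 and 5.5:** reconcile the current-pain definition with the pain-during-procedure question, so that the two are recorded as separate items. The form text should be checked, since a form carrying the 5.5 wording could not be used before anesthesia as it stands.
- **6.12:** report the paired change from pre-procedure to 3 months with a 95% CI, alongside the Soreness/pain categories at the same times.
- **Participants already treated without a pre-procedure mark:** describe the 3-month score as current nasal pain only.

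The cost is one extra 100 mm line at a visit already scheduled and a minor wording change, with no added visit or procedure. With no control arm, the paired change would account for pain present beforehand but would not separate procedural pain from other changes over the 3 months. The report should say so.
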